4.12.2 Toxin Neutralizing Activity (TNA)

Toxin neutralizing activity titers will be collected at weeks 4, 8 and 26 after the first AVA dose. The geometric mean titers (GMT) with corresponding 95% CI will be summarized for each treatment group at each timepoint. There will be no imputation for subjects with missing data at a given timepoint.

The percentage of subjects, with corresponding 95% CI, who seroconvert, defined as a ≥ 4 -fold increase in TNA titer will be summarized, at Weeks 4, 8, and 26 after the first AVA dose for both arms separately.

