4.4. Design Justification

This is a Phase 4 study to evaluate the immunogenicity of SC-administered AVA when administered alone or concomitantly with a single IV raxibacumab dose, in healthy adult volunteers who have not previously been immunized against the PA of *B. anthracis*. Subjects will receive the first AVA dose immediately after completion of a single 40 mg/kg raxibacumab IV infusion. Although this is an open-label study, measures have been introduced to minimize bias (refer to Section 6.3).

As a passive anti-toxin antibody, raxibacumab is expected to provide protection against PA for up to 28 days post dose [Migone, 2009]. The expected, but currently unapproved, use of AVA in combination with raxibacumab would be in the post-exposure prophylaxis setting. In that setting, raxibacumab would provide the initial toxin neutralizing activity while AVA immunization would generate a durable, toxin neutralizing anti-PA Ab response that maintains protection beyond 28 days, since raxibacumab levels may not be adequate for protection for more than 28 days post-infusion. Relative to this, 93% of subjects administered SC AVA doses at Weeks 0, 2, and 4 had at least a 4-fold increase in TNA titer by Week 4, with higher titers than for intramuscular (IM) doses administered according to the same schedule [Marano, 2008]. Based on these findings, this study will utilize SC-administered AVA rather than IM-administered AVA because the immunogenicity of SC-administered AVA early in the immunization series (at week 4) is of primary interest. Because of a lack of assay specificity for TNA response due to AVA when raxibacumab is present, it is not possible to specifically evaluate a 4 fold increase in the TNA titer due to AVA in this study. However, GSK developed analytical techniques which allow specific determination of anti-PA Ab concentrations in response to AVA vaccination, even in the presence of raxibacumab. Therefore, anti-PA Ab concentration will be assessed as the primary endpoint in this study, instead of >4-fold increase in TNA titers. Relative to this, a high correlation between anti-PA Ab levels and TNA has been reported [Crowe, 2010; Pittman, 2002; Pittman, 2005; Pittman, 2006; Quinn, 2004]. Thus, it is reasonable to expect that measurement of anti-PA Ab is reflective of a functional immune response.

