5.1. Inclusion Criteria

A subject will be eligible for inclusion in this study only if all of the following criteria apply:

1. Healthy as determined by the Investigator or medically qualified designee based on a medical evaluation including medical history, physical examination and laboratory tests
2. Men and women between 18 to 65 years of age
3. Willing and able to adhere to the procedures stated in the protocol.
4. Female subject is eligible to participate if she is not pregnant (as confirmed by a negative serum or urine human chorionic gonadotrophin (hCG) test), not lactating, and at least one of the following conditions applies:

A. Non-reproductive potential defined as:

- Pre-menopausal females with one of the following:
 - Documented tubal ligation
 - Documented hysteroscopic tubal occlusion procedure with follow-up confirmation of bilateral tubal occlusion
 - Hysterectomy
 - Documented Bilateral Oophorectomy
- Postmenopausal defined as 12 months of spontaneous amenorrhea [in questionable cases a blood sample with simultaneous follicle stimulating hormone (FSH) and estradiol levels consistent with menopause (refer to laboratory reference ranges for confirmatory levels)]. Females on hormone replacement therapy (HRT) and whose menopausal status is in doubt will be required to use one of the highly effective contraception methods if they wish to continue their HRT during the study. Otherwise, they must discontinue HRT to allow confirmation of post-menopausal status prior to study enrollment.

B. Reproductive potential and agrees to follow one of the options listed in [Appendix 3](#) requirements, the GSK Modified List of Highly Effective Methods for Avoiding Pregnancy in Females of Reproductive Potential (FRP), from 30 days prior to the first dose of study medication and until after the last dose of study medication and completion of the follow-up visit at Day 183 (at least five terminal half-lives for raxibacumab).

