9.4.2.2. Toxin Neutralizing Activity (TNA)

TNA titers will be collected at weeks 4, 8 and 26 after the first AVA dose. The GMTs along with 95% CI will be summarized for each treatment group at each timepoint. There will be no imputation for subjects with missing data at a given timepoint.

The percentage of subjects, along with 95% CI, who seroconvert, defined as a >4-fold increase in toxin neutralizing activity (TNA) titer will be summarized, at Weeks 4, 8 and 26 after the first AVA dose for both arms separately.

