2.1.2 Secondary Objective(s)

- To compare the immunogenicity of AVA at Week 8 and 26 after the first AVA dose, when AVA is administered alone or concomitantly with raxibacumab.
- To estimate and compare seroconversion, defined as a ≥ 4 -fold increase in toxin neutralizing activity (TNA) titer from baseline, at Weeks 4, 8 and 26 after the first AVA dose, when AVA is administered alone or concomitantly with raxibacumab.

- To describe the safety of AVA when co-administered with raxibacumab versus AVA alone.

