2.2.2 Secondary Endpoint(s)

- Ratio of GMC of anti-PA Ab at Weeks 8 and 26 after the first AVA dose, between the AVA alone and the AVA with raxibacumab treatment groups.
- Percentage of subjects who seroconvert, at Weeks 4, 8, and 26 after the first AVA dose, between the AVA alone and the AVA with raxibacumab treatment groups.
- Rates of reported adverse events (AE) as well as review of vital signs, urinalysis, and clinical laboratory data in the AVA alone and the AVA with raxibacumab treatment groups.

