	pre-raxi infusion	0 hr	0.5 hr (\pm 5 min)	2-6 hrs	Day 15 (\pm 2 days)	Day 29 (\pm 2 days)	Day 57 (\pm 2 days)	Day 183 (\pm 4 days)		
Inpatient visit		X								
Outpatient visit						X				
Urinalysis										
Admit to unit	X									
Randomization	X									
Discharged from unit				X					The subject will be discharged from the unit after all assessments are completed.	
Vital signs	X			X	X	X	X			
Hematology and clinical chemistry	X				X	X			Refer to Table 4 in CSP [1] for specific laboratory test. On Day 29 the specimen will be collected prior to treatment administration.	
Review concomitant medications	X				X	X	X	X		
Serum or urine pregnancy test	X				X	X	X	X		
Diphenhydramine administration		X							Diphenhydramine (25-50 mg) must be administered within 60 minutes prior to the raxibacumab infusion.	
Raxibacumab administration			X						Raxibacumab infusion must be completely administered prior to first AVA dose on Day 1 and administered in opposite limb from AVA injection.	
AVA administration			X		X	X			Each sequential AVA injection will be administered in a different injection site (eg. alternating arms).	
AE/SAE assessment	X	X	X	X	X	X	X	X		
PK sampling		X	X	X	X	X	X	X	A blood specimen will be collected prior to raxibacumab infusion, 30 minutes post raxibacumab infusion (\pm 5 min), 2-6 hours post infusion on Day 1, and at Days 15, 29, and 57 (14, 28, and 56 days post raxibacumab administration). An additional sample will be collected at the Day 183 visit.	
Anti-raxibacumab Ab	X					X	X			
Toxin Neutralizing Ab (TNA)	X					X	X	X	The Day 29 specimens will be collected prior to AVA administration.	
Anti-PA Ab	X					X	X	X	The Day 29 specimens will be collected prior to AVA administration.	

a. Day -1 is the calendar day preceding Day 1; the designation "Day 0" is not used in this study.

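### The Week 4 TNA seroconversion rate in the raxibacumab arm can include passive antibody that the protocol says cannot be separated from the AVA response

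*SAP*

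**What the plan says.** Protocol 4.4 states the limitation directly. Because the TNA assay cannot tell AVA-induced activity from raxibacumab, "it is not possible to specifically evaluate a 4 fold increase in the TNA titer due to AVA in this study". Anti-PA concentration was made primary for that reason. The same section says "raxibacumab is expected to provide protection against PA for up to 28 days post dose", and describes raxibacumab as the source of the initial neutralizing activity. It also explains that the 26-week duration was chosen so that AVA immunogenicity, TNA included, could be assessed once raxibacumab had been essentially eliminated. More than 99% of subjects are expected to have less than 5% of the dose left by Week 24.

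The objectives, endpoints and analysis sections do not carry this through:

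- SAP 2.1.2 sets the secondary objective "To estimate and compare seroconversion" with and without raxibacumab. SAP 2.2.2 gives the endpoint as "Percentage of subjects who seroconvert, at Weeks 4, 8, and 26 after the first AVA dose". Protocol section 3 matches both.
- SAP 4.12.2 says the percentage who seroconvert "will be summarized, at Weeks 4, 8, and 26 after the first AVA dose for both arms separately". Protocol 9.4.2.2 tabulates the same visits by arm. Neither adds a caveat.
- SAP 4.1 sets the TNA baseline at Day 1 before any study drug.
- SAP 3.2 subtracts serum raxibacumab from the anti-PA assay result and states no equivalent step for TNA.
- Protocol 7.3 leaves TNA assay details to the Study Reference Manual, which is not among the documents.

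The threshold also differs: protocol 9.4.2.2 requires more than a 4-fold rise, while SAP 4.12.2 and the objectives require at least 4-fold.

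**The concern.** Only Group 2 receives raxibacumab, and its baseline sample precedes the infusion. Any neutralizing activity that raxibacumab still contributes at a later visit counts towards the 4-fold rise in that arm and never in the other. The error has one direction: it raises the Group 2 rate and narrows any apparent deficit against AVA alone. The study exists to detect such a deficit, as a post-marketing commitment, so a reassuring Week 4 TNA table would be open to misreading. It would be set out as seroconversion, under an objective that compares the arms, although the protocol says an AVA-specific reading cannot be made.

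**Working it through.** **No plan figure to reproduce.** The documents give no power, precision or expected Group 2 rate for TNA. The check is one of timing, then of what can and cannot be bounded.

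**Step 1: timing.** The SAP schedule (Table 2.3) places PK samples "at Days 15, 29, and 57 (14, 28, and 56 days post raxibacumab administration", and TNA is drawn at the last two of these visits. The Week 4 sample thus falls at the end of the period for which protocol 4.4 still expects protection. With the ±2-day visit window, some samples fall inside it. Nothing comparable is stated for Day 57.

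**Step 2: how much drug could remain.** No half-life is given. Protocol 5.1 gives a limit by requiring contraception until "completion of the follow-up visit at Day 183 (at least five terminal half-lives for raxibacumab".

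- Day 1 to Day 183 is 182 days, so the terminal half-life is at most 182/5 = 36.4 days.
- Cross-check from protocol 4.4: under 5% at Week 24 (168 days) gives at most 168/log2(20) = 38.9 days.
- Fraction remaining = 0.5^(t / half-life), assuming mono-exponential decay.

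| Half-life (days) | Week 4 (28 d) | Week 8 (56 d) | Week 26 (182 d) |
|---|---|---|---|
| 10 (assumed) | 14.4% | 2.1% | 0.0% |
| 20 (assumed) | 37.9% | 14.4% | 0.2% |
| 36.4 (limit, 5.1) | 58.7% | 34.4% | 3.1% |
| 38.9 (limit, 4.4) | 60.7% | 36.8% | 3.9% |

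These are percentages of dose, not of TNA signal. The documents do not say what raxibacumab level produces a 4-fold TNA rise.

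**Step 3: illustration of the effect on the rate.** Let q be the Group 2 rate due to AVA and p the share who would reach a 4-fold rise from raxibacumab alone, independently of their AVA response. The observed rate is p + (1 − p)q, so the gap is understated by p(1 − q). Both p and q are assumptions. The comparator is the 93% that protocol 4.4 cites for AVA alone at Week 4.

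| p | q = 80%: observed, apparent gap | q = 50%: observed, apparent gap |
|---|---|---|
| 0% | 80%, 13 points | 50%, 43 points |
| 25% | 85%, 8 points | 62.5%, 30.5 points |
| 50% | 90%, 3 points | 75%, 18 points |
| 100% | 100%, −7 points | 100%, −7 points |

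At p = 0 there is no bias. At p = 100% the loss disappears entirely. The documents do not place p within that range.

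**Step 4: precision of a Week 26 comparison.** Approximate 95% half-width for a difference in proportions, with equal rates in both arms:

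- 267 per arm: 1.96 × √(2r(1 − r)/267) gives 4.3 points at r = 0.93 and 8.5 points at r = 0.50.
- 15 per arm (a stop at interim 1), Newcombe: half-width = √((p̂ − L)² + (U − p̂)²), with L and U the Wilson limits. For 14/15 in each arm (93.3%; 70.2% to 98.8%) it is √(0.2315² + 0.0548²) = 23.8 points. For 8/15 (53.3%; 30.1% to 75.2%) it is √(0.2322² + 0.2186²) = 31.9 points.

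**The case against.** The strongest reply is that the plan already knows this. Protocol 4.4 states the limitation, moves the primary endpoint to anti-PA and sets the study length so that TNA can be read after elimination. SAP 4.12.2 does not attribute the rate to AVA, specifies no between-arm test, and tabulates the arms separately (protocol 9.4.2.2: "will be summarized, at Weeks 4, 8 and 26 after the first AVA dose for both arms separately"). Group 2 raxibacumab concentrations will be listed and summarized at every visit (SAP 4.8 and 4.12.3). On this view a footnote is enough.

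Much of this stands. The table is descriptive, and a loss of response would show in the raxibacumab-subtracted Week 4 anti-PA result. But the objective still commits to comparing seroconversion at Week 4, and PK summaries elsewhere in the report do not stop two adjacent percentages from being read as response to AVA.

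A second objection is that the Week 8 versus Week 26 split is not proved by the figures: with a 10-day half-life, Week 8 carry-over (2.1%) is below the Week 26 upper limit (3.1%). That is correct across different half-lives. For any one half-life, however, Week 26 is far lower (34.4% against 3.1% at the limit), and Week 26 is the visit the protocol itself chose.

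A third is that quantifiable drug does not establish a passive 4-fold rise. That is also correct, so the proposed count can show only whether raxibacumab was present.

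A reader might also infer that Week 8 is contaminated, that the Week 4 rate is certainly inflated, or that the non-inferiority result or futility stops are compromised. The documents support none of these. Week 8 carry-over is only possible, no TNA potency is given, and the primary and interim analyses use anti-PA.

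**Conclusion.** The concern holds for Week 4. If the plan is followed exactly, the Group 2 Week 4 seroconversion rate can include passive raxibacumab activity and so understate a loss of AVA response, contrary to the protocol's own statement of what the assay can show. This rests on protocol 4.4 and on the absence of a stated TNA correction. A correction in the Study Reference Manual cannot be excluded, though protocol 4.4 says AVA-specific evaluation is not possible. Week 8 remains an open possibility.

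The size is unknown; the p and q figures only illustrate a range. The harm is confined to secondary descriptive TNA results, including the titers summarized in the same section. It should be corrected before analysis but does not threaten the main conclusion.

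The anti-PA results at Weeks 8 and 26 are probably raxibacumab-subtracted too, but SAP 3.2 ties the subtraction to the primary analysis and SAP 4.12.1 does not mention it, so that is an inference.

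**What to change.** In the secondary objective and endpoint, protocol 9.4.2.2 and SAP 4.12.2:

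1. Make Week 26 the visit for AVA-attributable TNA seroconversion and for any between-arm comparison, as a difference in proportions with a 95% CI by a score-type method such as Newcombe. Note that wash-out here means under 5% of the dose, not zero.
2. Keep the Week 4 and Week 8 TNA summaries, but label Group 2 as total neutralizing activity (raxibacumab plus AVA).
3. Beside each Group 2 TNA summary, give the number of subjects with quantifiable serum raxibacumab at that visit, noting that this does not by itself indicate a passive 4-fold rise.
4. Base statements about early AVA response on the raxibacumab-subtracted Week 4 anti-PA result, and state in SAP 3.2 and 4.12.1 that the same subtraction applies at Weeks 8 and 26.
5. Use one fold-rise threshold throughout.

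The cost is a wording amendment to one secondary objective and endpoint of a post-marketing commitment, SAP text, table labels, one count per visit from PK samples already scheduled, and one Week 26 estimate. If the amendment is slow, the labels and counts can go into the SAP first.

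What is given up is an AVA-attributed TNA comparison at Weeks 4 and 8. Missing Week 26 samples would widen the interval, since none are imputed. After a futility stop the Week 26 estimate may be imprecise, about ±24 to ±32 points at 15 per arm. It may not exist at all, because SAP 4.9 says the study will be terminated early and does not promise continued follow-up.

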As a secondary endpoint, ratios of the anti-PA Ab GMC for each treatment group at Weeks 8 and 26 will be calculated as described above.

TNA geometric mean titers (GMTs) along with 95% CI will be summarized for each treatment group at each timepoint. The percentage of subjects, along with 95% CI, who seroconvert, defined as a >4-fold increase in TNA titer will be summarized, at Weeks 4, 8 and 26 after the first AVA dose for both arms separately.

Clinical safety observations will include AEs, urinalysis, vital sign measurements, and clinical laboratory assessments. Safety data will be tabulated and, where appropriate, analyzed by the use of descriptive statistics. Safety data will be tabulated for the safety population.

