4.12 Secondary Analysis

4.12.1 Anti-PA Antibodies

Anti-PA antibody concentrations will also be collected at Weeks 8 and Week 26 after the first AVA dose. Values less than BLQ will be set to lower limit of quantitation (LLOQ). The GMCs with corresponding 95% CI will be summarized for each treatment group at each timepoint. No comparison between treatments will be made. There will be no imputation for subjects with missing data at a given timepoint.

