4.13 Changes from Analyses Planned in Protocol

Electrocardiogram intervals will be listed for only those subjects that had the procedure performed after experiencing an AE.

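### TNA seroconversion is to be compared between arms, but the planned analysis reports each arm separately and pre-specifies no between-arm estimate or interval

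*SAP*

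**What the plan says.** **Objective.** SAP 2.1.2 begins this objective "To estimate and compare seroconversion" and sets it at Weeks 4, 8 and 26. The protocol synopsis and Protocol section 3 carry the same objective.

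**Endpoint.** SAP 2.2.2 words it as a between-group quantity: "Percentage of subjects who seroconvert, at Weeks 4, 8, and 26 after the first AVA dose, between the AVA alone" and the AVA with raxibacumab groups. No effect measure is named.

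**Analysis.** Three places describe it, and all plan a percentage with a 95% CI in each arm:

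- SAP 4.12.2: "will be summarized, at Weeks 4, 8, and 26 after the first AVA dose for both arms separately"
- Protocol 9.4.2.2: "will be summarized, at Weeks 4, 8 and 26 after the first AVA dose for both arms separately"
- Protocol synopsis: "at Weeks 4, 8 and 26 after the first AVA dose for both arms separately"

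**Assay and timing.** Protocol 4.4 states that the TNA assay cannot isolate the response to AVA while raxibacumab is present. The same section sets the 26-week duration so that immunogenicity, TNA titer included, can be assessed after raxibacumab has essentially gone. It expects more than 99% of subjects to have less than 5% of the dose remaining by week 24.

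**Threshold.** Seroconversion is at least a 4-fold rise in the objectives of both documents and in SAP 4.12.2. It is more than a 4-fold rise in the analysis part of the synopsis and in Protocol 9.4.2.2.

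**The concern.** The objective has two verbs and the analysis serves only the first. Estimation within each arm is planned; comparison is not. No difference, ratio, odds ratio, test or between-arm interval for seroconversion appears in either document.

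This is a separate matter from the Week 8 and 26 anti-PA results, for which SAP 4.12.1 says "No comparison between treatments will be made". The synopsis does plan anti-PA ratios at those weeks, whereas no analysis text plans a contrast for seroconversion. Restoring the anti-PA ratio would therefore leave this objective unmet.

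At stake is the pre-specified reading of a functional response. Protocol 4.4 accepts anti-PA concentration as the primary endpoint partly because it correlates with TNA. Week 26 is when TNA can be read with little raxibacumab left. If the contrast is not fixed in advance, its method and lead time point would be chosen with the data in hand, in an open-label trial.

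**Working it through.** **1. The plan's own figure.** There is none for seroconversion: no margin, power, alpha or precision. The 534 subjects and 80% power belong to the primary endpoint. Recomputing that design with its two futility looks gives 79.99%, so it reproduces, and this point does not depend on it.

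**2. Inputs.**

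- n = 267 per arm: the Week 4 analyzable target (Protocol 4.3).
- AVA-alone rate of about 93%: a historical Week 4 figure (Protocol 4.4), taken as 248/267 = 92.9%.
- Combination-arm rates: assumed, because the documents give none.

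**3. Formulas**, with z = 1.96.

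- Wilson interval for one arm: [p + z²/2n ± z√(p(1−p)/n + z²/4n²)] / (1 + z²/n).
- Newcombe interval for d = p1 − p2, where (l, u) are the Wilson limits: from d − √[(p1−l1)² + (u2−p2)²] to d + √[(u1−p1)² + (p2−l2)²].

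**4. Example: 248/267 versus 232/267.** Here z²/n = 0.01439.

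- AVA alone, p1 = 0.9288: centre 0.9228, half-width 0.0312, interval 89.2% to 95.4%.
- Combination, p2 = 0.8689: centre 0.8637, half-width 0.0405, interval 82.3% to 90.4%.
- The arm intervals overlap between 89.2% and 90.4%.
- d = 0.0599.
- Lower limit: 0.0599 − √(0.0373² + 0.0353²) = 0.0599 − 0.0514 = 0.009.
- Upper limit: 0.0599 + √(0.0251² + 0.0458²) = 0.0599 + 0.0522 = 0.112.

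The difference is 6.0 points, 95% CI 0.9 to 11.2. It excludes zero although the arm intervals overlap.

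**5. How wide that zone is**, holding AVA alone at 248/267.

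| Combination arm | Difference (points) | Newcombe 95% CI | Arm intervals |
|---|---|---|---|
| 235/267 (88.0%) | 4.9 | −0.2 to 10.0 | overlap |
| 234/267 (87.6%) | 5.2 | 0.2 to 10.4 | overlap |
| 229/267 (85.8%) | 7.1 | 1.9 to 12.4 | overlap |
| 228/267 (85.4%) | 7.5 | 2.2 to 12.9 | separate |

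From 229 to 234 responders, the planned output looks inconclusive while the interval for the difference does not include zero.

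**6. Precision of the difference at equal rates.** Half-width = √[(p−l)² + (u−p)²].

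| n per arm | p | Wilson limits | Half-width (points) |
|---|---|---|---|
| 267 | 0.93 | 0.893, 0.955 | 4.5 |
| 267 | 0.80 | 0.748, 0.844 | 6.8 |
| 267 | 0.50 | 0.440, 0.560 | 8.4 |
| 225 (assumed attrition) | 0.93 | 0.889, 0.957 | 4.9 |
| 50 (stop at interim 2) | 0.93 | 0.825, 0.974 | 11.4 |
| 15 (stop at interim 1) | 0.93 | 0.698, 0.987 | 23.9 |

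The last two rows assume that the subjects already enrolled are still assessed. Protocol 4.4 calls Week 26 the nadir response, so the 4.5-point figure is close to a best case.

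**The case against.** **Comparing can be descriptive here.** Protocol 9.4.2.3 says that adverse event percentages will be compared, in a section that plans only tabulation and descriptive statistics. Side-by-side percentages fit that usage, and SAP 4.12.2 has no sentence barring comparison. This stands in part: an informal comparison is possible. It still supplies no interval for the contrast. Rewording the objective to estimate or describe would also reconcile the texts, but would give up the comparison.

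**The difference can be recovered.** SAP 4.1 requires n and percentage, so anyone can subtract the percentages and compute an interval. This stands. A reader might infer that the trial could not state the size of any loss; the documents do not support that. What is missing is a pre-specified estimate with its uncertainty.

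**The assay gives a reason for caution.** Protocol 4.4 is a plausible ground for not contrasting the arms at Week 4. This stands and limits the fix. Residual raxibacumab adds neutralizing activity in the combination arm and can mask interference. But neither analysis section cites this, the objective keeps all three weeks, and Week 26 was chosen to avoid it.

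**The SAP follows the protocol.** A reader might infer that the SAP dropped a planned comparison without declaring it, since SAP 4.13 lists only that "Electrocardiogram intervals will be listed for only those subjects that had the procedure performed after experiencing an AE". That reading fails: Protocol 9.4.2.2 plans the same separate-arm analysis, so there was no change to declare.

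**Conclusion.** The point holds as a mismatch between objective and analysis. Both documents set out to compare seroconversion between arms, and the synopsis, Protocol 9.4.2.2 and SAP 4.12.2 all stop at per-arm percentages. The primary conclusion, the sample size and the data collected are unaffected.

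Its size is illustrative. With 267 per arm and 248 responders on AVA alone, separate intervals obscure differences of about 5.2 to 7.1 points that the interval for the difference would show to exclude zero. These are Week 4 inputs. The documents give neither a Week 26 rate nor Week 26 attrition, so the half-width there could run from about 4.5 to 8.4 points at 267 per arm, and wider after a futility stop.

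A reader might also infer that seroconversion is the trial's only functional-antibody result. It is not: TNA geometric mean titers with 95% CIs are planned by arm as well. Nor would a difference at every week be attributable to AVA. On the documents' own account, only Week 26 is expected to be largely free of raxibacumab.

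**What to change.** In the synopsis, Protocol 9.4.2.2 and SAP 4.12.2, replace the separate-arms wording with the following:

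- **Estimate.** Report the percentage in each arm with its 95% CI, plus the difference (AVA alone minus AVA + raxibacumab) with a two-sided 95% CI by one named score-based method, Newcombe or Miettinen-Nurminen.
- **Status.** State that it is descriptive, with no margin and no multiplicity claim.
- **Lead time point.** Make Week 26 the lead comparison, citing the wash-out expected by week 24.
- **Caveat.** Label Week 4 as not AVA-specific under Protocol 4.4. Label Week 8 the same way unless raxibacumab is shown to be absent; the Day 57 PK samples already scheduled for Treatment Group 2 can inform that.
- **Threshold.** Use one seroconversion threshold in every place: either at least 4-fold or more than 4-fold.

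The cost is about one sentence in each place and one column in an existing table. No new data and no change to the sample size are needed. The risk is that an early-week difference is over-read, which the caveat is there to prevent.
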